9.4.2.1 Chemical Name and Formula of E2609

- Test drug code: E2609
- Generic name: not applicable
- Chemical name: International Union of Pure and Applied Chemistry
- *N*-{3-[(4*aS*,5*R*,7*aS*)-2-Amino-5-methyl-4*a*,5-dihydro-4*H*furo[3,4-*d*][1,3]thiazin-7*a*(7*H*)-yl]-4-fluorophenyl}-5-(difluoromethyl)pyrazine-2-carboxamide
- Molecular formula: C₁₉H₁₈F₃N₅O₂S
- Relative molecular mass: 437.44

9.4.2.2 Comparator Drug

Not applicable.

9.4.2.3 Labeling for Study Drug

E2609 will be labeled in accordance with text that is in full regulatory compliance with each participating country and is translated into the required language(s) for each of those countries. The following information may be included but is not limited to:

- Protocol number
- For clinical study use only
- Name and address of the sponsor
- Chemical name/drug identifier (ID)
- Lot number/batch number
- Storage conditions, expiration date if necessary

9.4.2.4 Storage Conditions

Study drug will be stored in accordance with the labeled storage conditions. Temperature monitoring is required at the storage location to ensure that the study drug is maintained within an established temperature range. The investigator or designee (or if regionally required, the head of the medical institution) is responsible for ensuring that the temperature is monitored throughout the total duration of the study and that records are maintained; the temperature should be monitored continuously by using either an in-house validated data acquisition system, a mechanical recording device, such as a calibrated chart recorder, or by manual means, such that minimum and maximum thermometric values over a specific time period can be recorded and retrieved as required.

9.4.3 Method of Assigning Subjects to Treatment Groups

Subjects will be assigned to treatments based on a computer-generated randomization scheme. The randomization scheme and identification for each subject will be included in the final clinical study report for this study. The doses and number of treatment groups to be used for Stage A (all subjects), for Stage B MCI/Prodromal subjects and Stage B for mild to moderate AD subjects are described in [Section 9.4.1](#). (revised per Amendment 01)

Randomization will be performed centrally by an IxRS. The IxRS or clinical supply vendor will generate the randomized blister card identification numbers. At enrollment, the investigator or designee will call the IxRS to register the subject information. At randomization (Visit 3), the IxRS will assign each subject a unique randomization number.

9.4.4 Selection of Doses in the Study

It is not known how the level of CSF or brain A β reduction is related to clinical efficacy. Therefore, in this study, doses will be selected such that at steady state, they will result in 25%, 50%, and 75% reduction in CSF A β levels from baseline to cover a broad range of PD effects.

In Study 007, the relative bioavailability of a tablet formulation of E2609 in the fed and the fasted states compared with the capsule formulation in the fasted state (used in Studies 001 and 002) was investigated. It was found that when the tablet form of E2609 (50 mg) was administered with food, the exposure (ie, AUC) of the parent drug E2609 was higher, with lower maximum observed concentrations and reduced exposure to the metabolites, compared with either formulation in the fasted state.

Based on the PK/PD modeling using data from healthy volunteer Studies 001, 002, and 007, doses of 5 mg, 15 mg, and 50 mg QD administered as the tablet formulation with food in this study should achieve CSF A β reduction from baseline of approximately 25%, 50%, and 75% at steady state, respectively ([Table 3](#)).

Table 3 Predicted Steady State Plasma PK Parameters and CSF Amyloid β Reduction From Baseline

| E2609 Tablet Daily Dose (mg) With Food | E2609 Plasma $C_{max,ss}$ (ng/ml) | E2609 Plasma $C_{ss,av}$ (ng/ml) | E2609 Plasma $AUC_{(0-24h)ss}$ (ng.h/ml) | % Reduction CSF BACE1 Activity | % Reduction CSF $A\beta(1-x)$ |
|---|---|--|--|---------------------------------------|---|
| 5 | 6.2 | 3.3 | 80.3 | 16.2 | 33 |
| 15 | 18.6 | 10 | 240.9 | 36.6 | 56 |
| 50 | 62.1 | 33.5 | 803.0 | 65.7 | 79 |

$A\beta(1-x)$ = amyloid beta monomer from amino acid 1 to x, $AUC_{(0-24h)ss}$ = area under the concentration x time curve at steady state from time zero to 24 hours, BACE1 = Beta-amyloid converting enzyme, CSF = cerebrospinal fluid, $C_{ss,av}$ = average steady-state concentration, $C_{max,ss}$ = maximum plasma concentration at steady state, PK = pharmacokinetics.

The PK/PD modeling described above, which was conducted using data obtained from healthy volunteers, has also been supported by modeling of data from subjects with an underlying AD pathology (Study 101). Furthermore, external data with another BACE1 inhibitor (MK-8931) showed a similar PD effect in AD patients as in healthy volunteers (Forman, et al., 2013). Therefore we are confident that the modeling of E2609 effects in healthy subjects will be applicable for both MCI/Prodromal and mild to moderate AD dementia patients. (revised per Amendment 01)

The exposure of the highest dose in this study (50 mg QD tablet administered with food) is less than that of the 100 mg QD dose (capsule administered fasted) in Study 002.

The 100 mg QD dose administered for 14 days in Study 002 was well tolerated with no clinically significant changes in laboratory parameters, vital signs, or ECG parameters. On Day 15, for the 100 mg QD cohort in Study 002, there was a reduction of CD4 lymphocyte counts compared with placebo (CD4 lymphocyte counts on E2609 decreased by 3.1% from baseline, whereas the placebo control showed an increase of 8.7%), but this decrease was less than that observed at doses of 200 mg (22.9% decrease) or 400 mg (17.3% decrease). No subjects had infections or drug rash while receiving E2609 100 mg QD or at lower doses in Study 002, whereas at 200 mg and 400 mg QD, 4 subjects had symptomatic orolabial HSV1 relapses and 2 subjects at the highest dose had drug rash. The highest dose for Study 202 of 50 mg QD (tablet administered with food) is therefore expected to have a similar or better safety profile compared with the 100 mg QD capsule (administered fasted) in Study 002. Specific exclusion criteria, blinded and unblinded safety monitoring procedures, and safety criteria for discontinuation from study drug are included in this study in order to mitigate any immunology-related risk with E2609, particularly in light of the progression from 14 days of dosing (Study 002) to 18 months of dosing in this study.

In Stage A, all subjects will be randomized to receive either placebo or E2609 at 5 mg, 15 mg, or 50 mg QD. In Stage B, subjects in the MCI/Prodromal cohort will continue to be randomized to receive either placebo or E2609 at 5 mg, 15 mg, or 50 mg QD. In Stage B, subjects in the Mild to Moderate AD cohort will be randomized to receive either placebo or E2609 at 15 mg or 50 mg QD, but not the 5-mg QD dose. The rationale for not including an E2609 5-mg QD dose in the dose regimens for Stage B subjects with mild to moderate AD is

that more advanced disease may require greater reduction in CSF A β levels for comparable effects. (revised per Amendment 01)

After 60 subjects in Stage A have completed 4 weeks of treatment, an interim analysis of the E2609 PK and PD profiles will be used to confirm the E2609 doses to be used for Stage B, where PD is measured as reductions from baseline in CSF A β (1-x) levels. (revised per Amendment 01) If the 95% confidence interval of the mean percentage change from baseline in CSF A β (1-x) measured after 4 weeks of treatment with a dose of E2609 does not include its intended target value (ie, 25%, 50%, and 75% reductions from baseline, respectively for E2609 at 5 mg, 15 mg, and 50 mg), PK/PD modeling will be conducted. This PK/PD modeling will use the observed PK and PD data from Stage A and will relate the average steady state plasma concentration of E2609 to steady state CSF A β (1-x) percentage reduction from baseline after 4 weeks of dosing. From this model, the new target plasma steady state concentrations of E2609 required to achieve the target levels of CSF A β (1-x) reduction will be estimated again. Dose adjustment for Stage B may be considered if it is possible to get closer to the new target plasma steady state concentrations of E2609 required to achieve the intended target levels of CSF A β (1-x) reduction than is possible with the initially planned doses, given the limitation that E2609 dose adjustments will have to be in 5-mg increments or decrements. Subjects already randomized to a dose that needs to be adjusted will be switched to the new adjusted dose and complete their treatment at this new dose.

If dose adjustment is required for Stage B, a protocol amendment reflecting the new doses will be submitted.

9.4.5 Selection and Timing of Dose for Each Subject

E2609 is administered orally, QD, with food. Study treatment will begin on Day 1 following randomization and will continue for approximately 78 weeks.

9.4.6 Blinding

E2609 and placebo will be administered as tablets of identical appearance.

During the Randomization Phase and Follow-Up Phases, subjects and all personnel involved with the conduct and interpretation of the study, including investigators, site personnel, and Eisai staff will be blinded to the treatment codes (double-blind).

Every effort should be made to keep the site staff responsible for reviewing laboratory reports and assessing AEs separate from the site staff responsible for the efficacy assessments, particularly for the CDR (ie, those who are trained and certified to perform the various cognitive assessments that are undertaken in this study). Furthermore, at the site, the notes and reports relating to safety assessments must be kept separate from the notes and reports relating to efficacy, particularly for the CDR. (revised per Amendment 01)

Randomization data will be kept strictly confidential, filed securely by an appropriate group with the sponsor or CRO and accessible only to authorized persons (eg, Eisai Global Safety) until the time of unblinding, per the standard operating procedure.

The PK/PD interim analysis to confirm the E2609 doses to be used for Stage B will be conducted by an independent group. Any changes to dose will be reflected in an amendment to the protocol and the Statistical Analysis Plan will detail how data will be handled in the primary analysis.

In the event that emergency conditions require knowledge of the study treatment given, the blind may be broken via the code breaker facility within the IxRS. Emergency procedures for revealing drug codes are given in [Section 9.5.4.5](#). If possible, before breaking the blind, the investigator should consult with the sponsor to ascertain the necessity of breaking the code.

At the conclusion of the study, all unused drug supplies are to be returned to the Eisai approved contract packaging vendor.

9.4.7 Prior and Concomitant Therapy

Medication (including over-the-counter medications) or therapy administered to the subject before the study (within 6 months of randomization) and during the study (starting at the date of informed consent) will be recorded on the Prior & Concomitant Medication eCRF or Non-Pharmacological Procedures eCRF. The investigator will record on the Adverse Event eCRF any AE for which the concomitant medication/therapy was administered. If the concomitant medication/therapy is being administered for a medical condition present at the time of entry into the study, the investigator will record the medical condition on the Medical History and Current Medical Condition eCRF.

Listings of prohibited and permitted drugs are provided in [Appendix 2](#). Prohibited medications are presented in [Listing 1](#), [Listing 2](#), [Listing 3](#), [Listing 4](#), [Listing 5](#), and [Listing 6](#). Medications that are permitted with restrictions are listed in [Listing 7](#), [Listing 8](#), and [Listing 9](#).

The following agents are not permitted before randomization (specific timeframes are shown below) and throughout the study until after the last treatment visit:

- Anticoagulants (eg, warfarin, digabatin) are not permitted for a period of 5 half-lives or 7 days (whichever is longer) before randomization
- Drugs which may cause QTc prolongation are not permitted for a period of 5 half-lives or 14 days (whichever is longer) before randomization
- Strong CYP3A4 inhibitors are not permitted for a period of 5 half-lives or 14 days (whichever is longer) before randomization
- Live vaccines are not permitted within 3 months before randomization. This does not apply to non-live/inactivated vaccines
- Ig therapy and biologic drugs are not permitted within 6 months before randomization

- Systemic or ocular immunosuppressive or immunomodulatory drugs are not permitted for a period of 5 half-lives or 60 days (whichever is longer) before randomization

Subjects taking AChEIs or memantine must meet the following criteria in order to be included in the primary analyses:

- On a stable dose for 12 weeks before the Baseline cognitive assessments at Visit 2
- Remain on a stable dose while on study

Subjects who initiate treatment with an AChEI or memantine during the study, or who change their dose of AChEI or memantine while on study, will be allowed to continue in the study, but their clinical efficacy data will be censored from the time of drug initiation for the primary analyses.

Subjects taking all other non-prohibited concomitant medications must meet the following requirements:

- Must be on stable dose for at least 4 weeks before randomization, except for medications that are administered as short courses of treatment or which are to be used intermittently as needed
- Medications that are used as needed, rather than on a stable daily basis, and which are central nervous system (CNS) active and may affect cognitive function, are not permitted during a period of 72 hours before cognitive testing

Subjects who initiate treatment with or have dose adjustment of drugs not intended for treatment of cognitive impairment during the study may continue in the study if in the opinion of the investigator this will not interfere with study procedures or subject safety, and are not prohibited above. If the subject initiates treatment for co-morbidities with a (non-prohibited) drug that may affect cognitive function, the subject should not have cognitive assessments performed until the dose has been stable for at least 4 weeks.

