| Staphylokinase | Eskinase, Heberkinasa Kabikinase, Streptase, Thrombosolv, Zykinase |
| Streptokinase | Streptase |
| Tenecteplase | TNKase |
| Tinzaparin | Innohep |
| Urokinase | Abbokinase, Kinlytic |
| Warfarin | Coumadin, Jantoven |
| Antiplatelet drugs | |
| Aspirin and Plavix (revised per Amendment 01) | 
For subjects who consent to CSF sample collection: Aspirin or clopidogrel is permitted in all subjects. Aspirin and clopidogrel in combination is not permitted. (revised per Amendments 01 and 02)
 
For subjects who do not consent to CSF sample collection: Aspirin and clopidogrel, individually or in combination, is permitted. (revised per Amendment 02)
 |

Note: This list is not exhaustive.

Listing 3 Prohibited Medications Within 5 Half Lives or 60 Days, Whichever is Longer, Before Randomization and Until after the Last Treatment Visit

| Generic name | Brand name (Names shown are not exhaustive and are examples only; names may be the ® or ™) |
|---|--|
| Systemic Immunosuppressants^a and Immunomodulatory therapy | |
| Azathioprine | Azasan, Imur |
| Ciclosporine | Gengraf, Neoral |
| Dexamethasone | Decadron, Dexasone, Diodex, Hexadrol, Maxidex |
| Fingolimod | Gilenya |
| Methotrexate | Trexall |
| Methylprednisolone | Medrol, Meprolone |
| Mycophenolate | CellCept, Myfortic |
| Prednisolone | Deltasone, Prednicot, Prednisone Intensol, Rayos, Sterapred, Sterapred DS |

Note: This list is not exhaustive.

a: Topical and inhaled formulations with minimal systemic exposure need not be prohibited.

Listing 4 Prohibited Medications Within 6 Months Before Randomization

| Generic name | Brand name (Names shown are not exhaustive and are examples only; names may be the ® or ™) |
|---|---|
| Immunoglobulin therapy | |
| Adalimumab | Humira |
| Bevacizumab | Avastin |
| Efalizumab | Raptiva |
| Etanercept | Enbrel |
| Immune globulin IV, IVIG, IGIV | Carimune, Flebogamma, Gamimune N, Gammagard, Gamunex, Gammar-P IV, Iveegam, Octagam, Panglobulin, Vigam, Polygam S/D, Privigen, Sandoglobulin, Venoglobulin-S |
| Infliximab | Remicade |
| Omalizumab | Xolair |
| Ranibizumab | Lucentis |
| Other monoclonal antibodies not listed here | |

Note: This list is not exhaustive.

Listing 5 Prohibited Live Vaccines Within 3 Months Before Randomization Until after the Last Treatment Visit (this does not apply to non-live/inactivated vaccines)

| Bacterial vaccines | Viral vaccines |
|---|---|

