9.1.1 Prerandomization Phase

The Prerandomization Phase includes a Screening Visit and a Baseline Visit. All Screening Visit assessments must be completed and eligibility to progress must be confirmed before any Baseline Visit assessments are performed. All Screening Visit and Baseline Visit assessments must be completed within 50 days and a window of 7 to 10 days is to be observed between the completion of all Baseline Visit assessments and randomization into the study at Visit 3. Thus, the Prerandomization Phase will last for up to 60 days. The series of assessments conducted during this phase will determine eligibility for randomization into the study.

Inclusion criteria are discussed in [Section 9.1](#) and detailed in [Section 9.3.1](#). Before randomization the clinician will provide a judgment on the classification of a subject as either MCI/Prodromal or likely mild to moderate AD. (revised per Amendment 01) This judgment may be discussed and reviewed with the Sponsor or Sponsor's representative, as necessary.

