9.1.1.2 Baseline Period

All Screening Visit assessments must be completed (and eligibility to progress confirmed) before any Baseline Visit assessments are performed. The Baseline Visit assessments (per [Table 6](#) and [Section 9.5.1.2](#)) are to be completed as soon as possible after completion of the final Screening Visit assessment (ie, PET scan) such that all Screening Visit and Baseline Visit assessments are completed within 50 days.

Inclusion and exclusion criteria will again be reviewed, vital signs including weight will be recorded, and a 12-lead ECG will be conducted in triplicate. A routine physical examination will be conducted and a dermatological assessment and neurological examination will be performed. A urine pregnancy test will be conducted for females of childbearing potential. Blood will be collected from all subjects for clinical chemistry and hematology, lymphocyte subset analyses, Ig analyses, and PD assessments. Blood samples will be collected and stored for determination of a subject's previous exposure to infective pathogens in the event of AEs that warrant further investigation occurring at a later point in the study. Psychometric assessments will be administered to the subject in the order stated in [Table 6](#). The caregiver or informant needs to be present at this visit. The Columbia Suicide Severity Rating Scale (C-SSRS) will also be administered ([Section 9.5.1.5.11](#)).

CSF will be obtained at this visit for PK and PD assessments (see [Section 9.5.1.5.3](#)).

Blood will be collected from all subjects for pharmacogenomic (PGx) analyses of apolipoprotein E (*ApoE*) and the *NAT2* phenotype of subjects enrolled in the study (see [Section 9.7.1.7.2](#)).

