10. Subjects with hepatic impairment, with total bilirubin greater than 1.5 \times upper limit of normal (ULN) or International Normalized Ratio (INR) greater than 1.7 at Screening or Baseline. Subjects with Gilbert's syndrome need not be excluded.
11. Any contraindications to MRI or PET scanning, including cardiac pacemaker/ defibrillator or ferromagnetic metal implants (eg, in skull; cardiac devices other than those approved as safe for use in MRI scanners). Subjects who require sedation for MRI or PET scanning as per local guidelines need not be excluded.
12. Any contraindications to lumbar puncture (LP) for CSF sampling (eg, lower spinal malformation on physical examination, local spinal infection or other abnormality, including but not limited to obesity)
13. Severe visual or hearing impairment that would prevent the subject from performing psychometric tests accurately
14. History of Ig deficiency or other immunodeficiency disorders (including subjects known to be human immunodeficiency virus positive)
15. Subjects with chronic viral hepatitis
16. A history of tuberculosis (TB). Subjects with no history of TB will be tested for previous TB exposure (eg, positive tuberculin skin test, interferon gamma release assay or other locally accepted tests) and a positive test will be exclusionary.
17. A history of ophthalmic shingles
18. A history of ocular herpes simplex virus (HSV) infection

19. Any live vaccine in the 3 months before randomization.
20. Any active infection within the last 4 weeks prior to randomization. For such cases, the timing of randomization can be extended (up to 4 weeks) to allow the infection to resolve; psychometric tests conducted at Visit 2 (eg, MMSE, CDR) must be repeated.
21. Any chronic inflammatory disease that is not adequately controlled or that requires systemic or ocular immunosuppressive or immunomodulatory therapy. Subjects with:
 - a. Seasonal or perennial allergic rhinitis, asthma or chronic obstructive pulmonary disease where the condition is considered to be stable and adequately controlled by inhaled steroids need not be excluded.
 - b. Hashimoto's thyroiditis but who are stable on thyroid replacement therapy and not on systemic immunosuppressive therapy need not be excluded.
 - c. Cutaneous manifestations of immunological disease that do not require systemic immunosuppressive therapy or systemic immunomodulatory therapy need not be excluded (topical steroid treatment is permitted).

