9.5.1.4.2 PHARMACODYNAMIC, PHARMACOGENOMIC, AND OTHER BIOMARKER, ASSESSMENTS

Biomarkers

Subjects will be encouraged to stay at the site after completion of LP for medical observation. At Baseline, a CSF sample will be collected by LP (gravity drip method) after fasting (preferred), or at least 2 hours after the most recent meal. The timing of the Baseline LP needs to be scheduled carefully such that subsequent LPs (Visit 7 and Visit 18) can be performed between 4 and 8 hours postdose and at a similar time of day (± 1 hour) for each individual subject. At visits where cognitive tests are also performed, if the tests are to be performed on the same day, the LP must be performed after the cognitive tests have been completed and the subjects should rest and drink some fluid to hydrate before the LP. (revised per Amendment 01) The CSF sample will not be taken at the ED Visit if this visit occurs within 3 months of a previous CSF sample. The CSF sample will be used for PD assessments including but not limited to CSF $A\beta(1-x)$, $A\beta(1-42)$, t-tau, p-tau, and BACE. The plasma sample will be used for $A\beta(1-x)$ analysis and may be used for exploratory biomarker analyses (eg, miRNA). $A\beta(1-x)$ in both CSF and plasma will be measured using a commercially based enzyme-linked immunosorbent assay (ELISA). The pre- and post-screening analysis of CSF $A\beta(1-42)$, t-tau, and p tau will be performed using ELISAs. BACE1 levels will be measured using internally developed fluorescence resonance energy transfer and ELISA based assay(s). Substrates of BACE1 inhibition may also be explored using Western blots or other amenable methodology if clinical observations warrant and if analytes can be reliably tested in samples collected.

The blood sample collected for PD analyses at Baseline should be collected on the same day shortly before or shortly after completing the LP at Baseline. The sample should be collected at fasting or at least 2 hours after the most recent meal. (revised per Amendment 01)

At the Baseline Visit, CSF and blood samples will be collected and stored for determination of prior exposure to any suspected infective agents in the event that the subject develops treatment-emergent AEs that warrant further investigation (eg, treatment-emergent infection). Testing may include, but not be limited to, serological tests, viral titer by quantitative polymerase chain reaction, or human leukocyte antigen genotyping.

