| Antipsychotic/ anti-emetic/ schizophrenia/ nausea | | |
| Chlorpromazine | Thorazine | |
| Gastrointestinal stimulant/ heartburn | | |
| Cisapride | Propulsid | |
| Antinausea/ nausea | | |
| Domperidone | Motillum | Not available in the United States |

Listing 1 Drugs with High Risk of Torsades de Pointes or QTc Prolongation

| Generic name | Brand name (Names shown are not exhaustive and are examples only; names may be the ® or ™) | Comments |
|--|--|---|
| Sedative; antinausea/ anesthesia adjunct, nausea | | |
| Droperidol | Inapsine | |
| Antibiotic; gastrointestinal stimulant/ bacterial infection; increase gastrointestinal motility | | |
| Erythromycin | Erythrocin; E.E.S. | Incidence in females greater than males |
| Antipsychotic/ schizophrenia | | |
| Haloperidol | Haldol | When given intravenously or at higher than recommended doses, risk of sudden death, QT prolongation, and torsades increases |
| Mesoridazine | Serentil | |
| Thioridazine | Mellaril | |
| Opiate agonist/ pain control, narcotic dependence | | |
| Levomethadyl | Orlaam | |
| Methadone | Methadose; Dolophine | Incidence in females greater than males |
| Anti-infective/ pneumocystis pneumonia | | |
| Pentamidine | Pentam; NebuPent | Incidence in females greater than males |
| Antipsychotic/ Tourette's tics | | |
| Pimozide | Orap | Incidence in females greater than males |
| Antilipemic/ hypercholesterolemia | | |
| Probucol | Lorelco | No longer available in United States |
| Anticancer | | |
| Arsenic trioxide | Trisenox | Used for leukemia |
| Vandetanib | Zactima | Used for thyroid cancer |

Note: This list is not exhaustive.

QTc = Corrected QT interval.

Listing 2 Prohibited Medications Within 7 Days (or 5 Half-lives, Whichever is Longer) Before Randomization and Until after the Last Treatment Visit)

| Generic Name | Brand name (Names shown are not exhaustive and are examples only; names may be the ® or ™) |
|---|---|
| Anticoagulants | |
| Adeporin | Normiflo |
| Alteplase, tPA | Activase, Cathflo Activase |
| Anisindione | Miradon |
| Antithrombin III | ATryn, Thrombate III |
| Argatroban | Argatroban |
| Bivalirudin | Angiomax |
| Dabigatran | Pradaxa |
| Dalteparin | Fragmin |
| Danaparoid | Orgaran |
| Dicumarol | Dicumarol |
| Enoxaparin | Lovenox |
| Fondaparinux | Arixtra |
| Heparin Sodium | Monoject |
| Lanoteplase | Lanoplase |
| Lepirudin | Refludan |
| Pentosan polysulfate sodium | Elmiron |
| Reteplase | Retavase, Retevase |

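### The anticoagulant restriction is counted back from randomization, but the Baseline lumbar puncture comes at least 7 days before randomization, so the 7-day limit guarantees no drug-free time before it

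*Protocol*

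**What the plan says.** **The restriction.** Section 9.4.7 reads: "Anticoagulants (eg, warfarin, digabatin) are not permitted for a period of 5 half-lives or 7 days (whichever is longer) before randomization". The synopsis repeats it. The heading of Listing 2 in Appendix 2 agrees and gives the end point too: "Prohibited Medications Within 7 Days (or 5 Half-lives, Whichever is Longer) Before Randomization and Until after the Last Treatment Visit".

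**The first puncture.** Section 9.1.1.2 says of the Baseline Visit: "CSF will be obtained at this visit for PK and PD assessments". Sections 9.5.1.3.3 and 9.5.1.4.2 make clear that this sample is taken by lumbar puncture, and Table 6 lists it under Visit 2.

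**The interval between them.** Section 9.1.1 states that "a window of 7 to 10 days is to be observed between the completion of all Baseline Visit assessments and randomization". Section 9.1.2 and the notes to Tables 6 and 7 say the same. Exclusion 20 in section 9.3.2 allows a longer gap after an active infection: "the timing of randomization can be extended (up to 4 weeks) to allow the infection to resolve". In that case it requires the Visit 2 psychometric tests to be repeated; it does not mention the lumbar puncture.

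These sections are from Version 3.0 (Amendment 01). Of the later version (Amendment 02) only the back part is shown. Its Listing 2 heading still counts from randomization.

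**The concern.** The restriction and the procedure are timed from different points. A washout of at least 7 days ending at randomization looks sufficient until the visit schedule is laid beside it: the puncture is already over when the 7 days begin, or takes place on the first of them. A candidate who stops an anticoagulant exactly when section 9.4.7 requires could still have been taking it up to the Baseline puncture, unless some other control intervenes.

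What is at stake is bleeding risk at an invasive procedure that Version 3.0 schedules for every subject at Baseline.

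The protocol does not say why anticoagulants are restricted. Two places suggest that lumbar puncture is at least part of the reason. In the later Listing 2, the antiplatelet rule opens with "For subjects who consent to CSF sample collection" and differs for those who do not consent. The Version 3.0 revision history explains an earlier change to the same antiplatelet entry by the need for CSF from all subjects. Elsewhere in section 9.4.7 the stable-dose rule for AChEIs and memantine is tied to Visit 2, so the section does use that visit as an anchor for another drug class.

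**Working it through.** This is timeline arithmetic, with randomization (Visit 3) as day 0.

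**Inputs**
- Restriction: the longer of 7 days or 5 half-lives before day 0 (section 9.4.7, synopsis, Listing 2).
- Screening and Baseline together: at most 50 days (section 9.1.1).
- End of Baseline to randomization: 7 to 10 days (section 9.1.1).
- Infection extension: up to 4 weeks, that is 28 days (Exclusion 20).

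**The plan's own figure.** 50 + 10 = 60 days, which reproduces the stated maximum length of the Prerandomization Phase.

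**Day of the Baseline puncture.** If it is done on the last Baseline day, it falls between day −7 and day −10. With the full extension, and assuming it is not repeated, it can fall at −(10 + 28) = day −38. If it is done before other Baseline assessments it falls earlier; the protocol gives no separate length for the Baseline Visit.

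**Where the 7-day limit governs.** It is the longer limit when 5 × half-life ≤ 7 days, so half-life ≤ 7 × 24 / 5 = 33.6 h. The restriction then starts on day −7.

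| Puncture on | Restriction starts after the puncture by | Guaranteed drug-free time before puncture |
|---|---|---|
| day −7 | 7 − 7 = 0 days | 0 days |
| day −10 | 10 − 7 = 3 days | 0 days |
| day −38 | 38 − 7 = 31 days | 0 days |

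**Where 5 half-lives govern.** With the puncture L days before randomization, the window reaches the puncture day when the half-life is at least L × 24 / 5 hours:
- L = 7: 33.6 h
- L = 10: 48.0 h
- L = 38: 182.4 h

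Reaching the day of the puncture is not a washout before it. For 7 drug-free days before the puncture the half-life would have to be at least (L + 7) × 24 / 5 hours: 67.2 h, 81.6 h and 216.0 h respectively.

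In general, the guaranteed drug-free time before the puncture is the length of the window minus L, or zero if that is negative. Since L is at least 7 days, it is always shorter than the window the rule itself names. With a half-life of 67.2 h, for example, the window is 5 × 67.2 / 24 = 14 days, and a puncture on day −7 has 14 − 7 = 7 drug-free days before it, not 14.

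The protocol gives no half-lives, so these are thresholds and not statements about any named anticoagulant.

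**The case against.** The strongest reply is that section 9.4.7 is not the only control.

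- **Exclusion 12** excludes subjects with any contraindication to lumbar puncture, and its examples are expressly not exhaustive. An investigator could apply it to current anticoagulant use, and eligibility and medication are reviewed again at Visit 2. It would be wrong to read this criterion as confined to spinal or local conditions.
- **Coagulation tests.** PT, PTT and INR are measured at Screening and Baseline, and eligibility from Screening must be confirmed before any Baseline assessment, so results exist before the first puncture. Exclusion 10 gives an INR limit of 1.7, but within a criterion on hepatic impairment; there is no exclusion limit for PT or PTT.

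Both stand as partial safeguards. Neither names anticoagulants or sets a drug-free interval, and a specific rule that permits use until 7 days before randomization could be taken as the governing one.

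A second reply is that the ban applies throughout the study, and that the study starts at consent. The consent date in section 9.4.7 governs the recording of medication. The sentence introducing the prohibited drugs limits the period before randomization to the timeframes it then lists, and the Listing 2 heading confirms that start.

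A third reply is that different anchors are not a formal contradiction and that the purpose of the restriction is inferred. That is fair. The mismatch in dates stands regardless.

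A reader might also infer a gap at the other end, because CSF may be taken at an Early Discontinuation Visit after the last dose. Table 7 groups that visit with the Treatment visits, before the Follow-Up columns, so the documents do not show such a gap. The restriction also covers the punctures at Visits 7 and 18.

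**Conclusion.** The point holds for the Baseline lumbar puncture only. For half-lives up to 33.6 h, the restriction as written starts 0 to 3 days after a puncture done on the last Baseline day, and up to 31 days after it with the full infection extension. It guarantees no anticoagulant-free time before that puncture. For longer half-lives it may cover the puncture day without guaranteeing a full washout.

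This rests on three assumptions: that the puncture is done no later than the last Baseline day, as section 9.1.1 implies; that it is not repeated after an infection delay; and that the restriction is meant, at least in part, to protect the puncture.

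Two stronger readings are not supported. One is that everyone who uses the permitted washout is exposed: the 5-half-life limit reaches the puncture day for some drugs, Exclusion 12 or the coagulation results may remove others, and the number of anticoagulated candidates is not given. The other is that the Baseline CSF reference values would be contaminated with blood; nothing in the documents addresses this. Whether the mismatch persists in the body of the Amendment 02 version cannot be checked, and there CSF collection appears to depend on consent.

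**What to change.** The sponsor should reconcile the anticoagulant restriction in section 9.4.7, the synopsis and Listing 2 with the timing of the Visit 2 lumbar puncture in Table 6, including the case where randomization is delayed under Exclusion 20. It should also state whether the restriction is intended to cover that puncture. The anchor and the length of any interval are for the sponsor's clinicians, and none is proposed here.

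The cost is a wording change in three places, with no added visit or test. Depending on what the clinicians decide, a few candidates may be delayed or excluded at an earlier stage.
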